### 12.5.6 Tertiary Variables

The following tertiary endpoints will be explored:

- All endpoints will be compared at all other time-points.
- Evaluation of durability of response and incidence of recurrence of treated warts from Week 18 end of post-treatment efficacy evaluation period to Week 30 the end of the follow-up period.

A. All endpoints at all other time-points, including

- 1) Proportion of subjects with complete clearance of all treated warts at
  - Week 2
  - Week 4

Comparison of the active group and vehicle will be done by the same method employed for the primary analysis on the same endpoint (i.e. CMH test).

- 2) Ratio of cleared warts to all treated warts for each subject at
  - Week 2
  - Week 4

Comparison of the active group and vehicle will be done by the same method employed for secondary analysis on the same endpoints (i.e. Wilcoxon rank sum test).

---

3) Reduction from baseline in wart size of total treated warts at

- Week 2
- Week 4
- Week 6
- Week 12

Comparison of the active group and vehicle will be done by the same method employed for secondary analysis on the same endpoints (i.e. ANCOVA).

B. Durability/Recurrence

- At Week 18, 3 groups of responders (non-responder, complete responder, and partial responder) will be summarized.

The summary of durability and recurrence will be presented for the subjects who are complete or partial responders at Week 18 and continue to Week 30 Follow up. For the complete responders at Week 18, the number and percentage of subjects with durable response, with non-durable response from Week 18 to Week 30 will be summarized. For partial responders at Week 18, new complete responder, partial response, and non-responder at week 30 will be summarized by group. Complete responders are defined as all treated warts cleared. Partial responders are defined as at least 1 but not all treated warts cleared. Non-responders are defined as no treated warts cleared. Recurrence is defined as any treated wart not cleared at Week 30 for a complete responder at Week 18. Total complete responders at Week 30 are defined as maintenance of complete response at Week 30 plus new complete responders at Week 30.

No formal hypothesis testing is planned for these tertiary analyses. Therefore, any statistical testing done will be considered to be descriptive and not inferential.

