#### **7.3.2.7. Follow-up# 1 (Week 24) Visit**

The Follow-up# 1 Visit is to occur at the end of Week 24 ( $\pm$  7 days). The following procedures will be performed during this visit:

1. Review and question subject and/or caregiver(s) about use of any restricted concomitant medications/treatments (refer to Section 7.6.10.1).
2. Perform wart assessments (refer to Section 7.4.1).
3. Confirm Follow-up #2 / Week 30 Visit.

- \* Remind the subject and/or caregiver(s) about restricted medications/treatments (refer to Section 7.6.10.1).

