### **7.7.6.3. Tertiary Endpoints**

- All endpoints will be compared at all other time-points.

- Evaluation of durability of response (clearance and/or wart size reduction) and incidence of recurrence of treated warts from Week 18/End of Post-treatment Efficacy Evaluation period to the end of the follow-up period (week 30).

These data are considered tertiary and exploratory to gain insight regarding the pharmacodynamic nature of the treatment response. No formal hypothesis testing is planned. Therefore, any statistical testing done will be considered to be descriptive and not inferential.

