## 12.5 Efficacy Analyses

The primary and secondary efficacy analyses are planned analyses and the tertiary analyses are exploratory only in order to gain insight regarding the pharmacodynamic nature of the treatment response.

Wart assessments are conducted at Screening, Baseline, Week 2, Week 4, Week 6/EOT, Week 12, Week 18/End of Post-treatment Efficacy Evaluation, and Week 30 Follow up (for the subset of subjects). Wart characterization categories (solitary and cluster/splitting/satellite), the total number of warts, and the location (hands: dorsal, periungual, and palmar; foot: dorsal, limbs: arm and leg; and trunk) will be tabulated for the baseline visit for the ITT analysis set, using descriptive statistics.

The changes from baseline in total wart sizes (mm) will be summarized by group and by visit. Clinical clearance of a wart, as determined by the PI or an appropriately qualified Sub-I, should be recorded with a size of 0 mm in the CRF.

Wart assessment data will be listed for all subjects.

New common warts that appear after the Baseline visit will be identified, characterized and location recorded/mapped only, but not treated in this study. Any new common warts will be summarized in ITT analysis set for descriptive purpose and listed by subject.

Clinical Photography information collected in the CRF will be listed.

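### SAP 12.5.6 reads recurrence at Week 30 only and in complete responders only, which is narrower than the Week 18 to Week 30 endpoint and may misstate durability

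*SAP*

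**What the plan says.** - **Endpoint.** Protocol 7.7.6.3 asks how durable the response is and how often treated warts recur, over the time between the Week 18 and Week 30 visits. SAP 7.3 and the opening of SAP 12.5.6 restate the same interval, and SAP 4.1 declares no changes from the protocol.
- **Who is followed.** Under Protocol 7.1, anyone with at least one treated wart cleared at Week 18 enters follow-up, so partial responders are included. The stated purpose is to evaluate recurrence and durability.
- **When warts are assessed.** Protocol 7.3.2.7: "The Follow-up# 1 Visit is to occur at the end of Week 24". Wart assessment is a listed procedure at that visit and again at Week 30, and SAP Table 1 agrees. The list of assessments in SAP 12.5, however, goes from Week 18 straight to the last item, "and Week 30 Follow up (for the subset of subjects".
- **How recurrence is counted.** SAP 12.5.6: "Recurrence is defined as any treated wart not cleared at Week 30 for a complete responder at Week 18". Durable and non-durable response are tabulated for complete responders without a separate visit-by-visit definition.
- **Partial responders.** "Partial responders are defined as at least 1 but not all treated warts cleared". Their only follow-up summary is this: "For partial responders at Week 18, new complete responder, partial response, and non-responder at week 30 will be summarized by group".
- **Denominator.** The summary "will be presented for the subjects who are complete or partial responders at Week 18 and continue to Week 30 Follow up".

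**The concern.** An incidence over a 12-week interval has become a status at one visit, in one of the two responder groups being followed. This has three consequences.

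1. A recurrence recorded at Week 24 does not count if the wart is clear again at Week 30.
2. A cleared wart that returns in a partial responder is never called a recurrence, and usually leaves the Week 30 category unchanged.
3. Nothing says what happens to a responder without a Week 30 visit, even when Week 24 already documented a recurrence. The LOCF and BOCF sensitivity analyses in SAP 12.5.2 are for the primary endpoint, and the imputation model there stops at Week 18.

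At stake is the credibility of the durability statement, which is what the follow-up period was added to support. No primary or secondary conclusion depends on it.

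**Working it through.** **The plan's own figures.** The documents state no recurrence, re-clearance or follow-up dropout rate. The relevant planning inputs (SAP 6.1) are complete clearance of 10% and 2%, with about 240 per group. These are the rates behind the stated power. With p̄ = 0.06 and two-sided α = 0.05:

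- Power = Φ[(0.08 − 1.96·√(2·0.06·0.94/n)) / √((0.10·0.90 + 0.02·0.98)/n)].
- n = 200: 92.4% (stated 92%). n = 240: 96.0% (stated 96%).

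Expected Week 18 complete responders are therefore 240 × 0.10 = 24 active and 240 × 0.02 = 4.8, about 5, on vehicle. Each subject is worth about 4 points in the active group (1/24 = 4.2%).

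**Complete responders: assumed illustration.** Take 24 active complete responders. Suppose 6 recur (25%), 3 of them by Week 24 and 3 later. Counting either visit over all 24, the durable share is 18/24 = 75.0%. The SAP rule gives the following. In the last three rows, subjects without a Week 30 visit are left out of the denominator.

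| What happens | Reported durable share |
|---|---|
| Every recurrence is still present and seen at Week 30 | 18/24 = 75.0% |
| 1, 2 or 3 of the Week 24 recurrences are clear again at Week 30 | 19/24 = 79.2%, 20/24 = 83.3%, 21/24 = 87.5% |
| 1, 2 or 3 of the Week 24 recurrers have no Week 30 visit | 18/23 = 78.3%, 18/22 = 81.8%, 18/21 = 85.7% |
| 20% of Week 24 recurrers and 20% of non-recurrers have no Week 30 visit | 0.60/(0.60 + 0.10 + 0.125) = 72.7% |
| Half of the 18 non-recurrers, and nobody else, have no Week 30 visit | 9/(9 + 6) = 60.0% |

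Re-clearance moves the share in one direction only. Missing visits move it in either direction, depending on who is missing.

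**Range over the assumed recurrence rate**, with half of the recurrences by Week 24:

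- All Week 24 recurrers lost: at 10% recurrence, 0.90/0.95 = 94.7% against 90.0% (+4.7 points); at 40%, 0.60/0.80 = 75.0% against 60.0% (+15.0 points).
- Half of the non-recurrers lost instead: at 10%, 0.45/0.55 = 81.8% (−8.2 points); at 40%, 0.30/0.70 = 42.9% (−17.1 points).

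**Partial responders.** Take a subject with 5 treated warts, 3 of them clear at Week 18. At Week 30, 0 clear is a non-responder, 1 to 4 clear is a partial response, and 5 clear is a new complete responder. Losing one or two of the three cleared warts changes nothing in the table. Nor does a relapse offset by clearance of another wart. Only a count of zero registers.

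**The case against.** - **The endpoint is tertiary, with no formal testing.** This stands and limits the severity. Status at the end of follow-up is also a defensible descriptive measure. It is not, however, the incidence over the interval that both documents name.
- **Partial responders are not left out.** This stands in part. Their Week 30 category is tabulated, total complete responders at Week 30 are reported, and complete loss of response shows as a non-responder. What is missing is partial or offset relapse.
- **Week 24 is not lost.** It is in the SAP's visit schedule, and all wart assessments are listed by subject. The plan to compare all endpoints at all other time-points might be read to include it. Yet the itemised time-points in SAP 12.5.6 do not name Week 24, so no tabulation is assured.
- **Nobody need be dropped from the denominator.** The phrase "complete or partial responders at Week 18 and continue to Week 30 Follow up" can mean entering follow-up, which is how Protocol 7.1 and SAP 12.0 speak of continuing. This stands: the text is ambiguous, and the last three table rows hold only on the narrower reading. The wider reading still leaves no rule for scoring a missing Week 30 visit.
- **Retreatment is controlled.** Other wart treatment is prohibited through follow-up and reviewed at both follow-up visits, so its use should be on record. SAP 12.5.6 does not say how such a subject is scored.

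**Conclusion.** The SAP's recurrence rule is narrower than the endpoint it serves, and the narrowing is not declared. Two effects follow from the text alone: a recurrence seen only at Week 24 is scored as durable, which can only raise the durable share, and most wart-level relapse in partial responders is invisible.

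A reader might go further and infer that durability is overstated. The documents do not support that. The treatment of missing Week 30 visits is ambiguous and can bias the share either way, and nothing in the documents shows that subjects whose warts return are the ones who leave. The supported conclusion is that durability may be misstated.

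The figures of 60.0% to 87.5% against 75.0% rest on an assumed 25% recurrence with half of it by Week 24, on assumed patterns of re-clearance and absence, and, at the lower end, on the narrower reading of the denominator. They show sensitivity and do not estimate the effect. Severity is minor.

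**What to change.** Before unblinding, amend SAP 12.5.6 and 12.5 as follows:

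1. Define recurrence as any treated wart recorded as 0 mm at Week 18 and above 0 mm at Week 24 or Week 30.
2. Report it per subject, with complete and partial responders shown separately, and per cleared wart.
3. Use all Week 18 responders (at least one cleared treated wart) as the denominator. Requiring any one follow-up visit would not be enough: it omits responders with none, and without a further rule it counts a subject clear at Week 24 and then lost as non-recurrent.
4. Count a Week 24 recurrence even when Week 30 is missing.
5. Show subjects with no observed recurrence and no Week 30 visit as a separate category, with bounds counting them all as recurrent and all as non-recurrent. In the 60.0% scenario above, the bounds on recurrence would be 6/24 = 25.0% and (6 + 9)/24 = 62.5%.
6. Add Week 24 to the assessment list in SAP 12.5.

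The data are already collected, so the cost is SAP wording and a few extra table rows. The durability figures may look somewhat less favourable, and the bounds will be wide if many Week 30 visits are missed.

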#### **12.5.7 Other Variables**

The number of new common warts will be presented by visit.

#### **12.6 Safety Analyses**

In general, missing data will not be imputed for safety analyses.

#### **12.6.1 Adverse Events**

Any condition, event and/or signs and symptoms occurring after signing the informed consent form and before starting study drug treatment should be recorded as medical history in the eCRF. Medical conditions/diseases are considered AEs only if they worsen after starting study drug treatment (first application of study drug).

Therefore, An AE includes any condition (including a pre-existing condition) that: 1) was not

---

present prior to study treatment, but appeared or reappeared following initiation of study treatment, or 2) was present prior to study treatment, but worsened during study treatment.

A treatment-emergent adverse event (TEAE) is defined as an AE with onset date at or after the first dose administration of treatment, but no more than 30 days after the last dose of study medication. Only TEAEs will be included in the summary tables.

Adverse events will be coded using MedDRA version 21.0, as applicable at time of analysis. All reported AEs will be coded to the appropriate SOC and PT according to MedDRA Version 21.0.

The relationship of an AE to study drug is to be assessed according to the following definitions:

- Not Related – no temporal association or the cause of the event has been identified, or the drug cannot be implicated based upon available information.
- Possibly Related – temporal association, but other etiologies are likely to be the cause. However, involvement of the drug cannot be excluded, based upon available information.
- Definitely Related – established temporal or other association (e.g., re-challenge) and event is not reasonably explained by the subject's known clinical state or any other factor, based on available information.

The severity of an AE is to be scored according to the following scale:

- Mild - Awareness of sign or symptom, but easily tolerated
- Moderate - Moderate Discomfort enough to cause interference with usual activity
- Severe - Severe Incapacitation with inability to work or perform usual activity

A high level overall summary of TEAEs will be presented to summarize AEs in any category.

Subject incidence of the following AEs will be tabulated by SOC (descending order of frequency) and PT (descending order of frequency). The number and percentage of each TEAE will be calculated.

- TEAEs
- severe TEAEs
- treatment-related TEAEs
- maximum severity of TEAEs
- TEAE with an outcome of death
- TEAE leading to discontinuation of study treatment
- TEAE leading to discontinuation of the study

Subject incidence of the following AEs will be tabulated by PT in descending order of frequency:

- TEAEs

---

- TEAEs experienced by  $\geq 2$  subjects (for any treatment)
- treatment-related TEAEs by  $\geq 2$  subjects (for any treatment)

Subjects will be counted only once within each SOC or PT. For tables categorized by severity, subjects with multiple events within a particular SOC or PT will be counted under the category of their most severe event for that SOC or PT. Treatment-related TEAEs included AEs from AE CRF page where relationship to study treatment is checked with either 'Possibly Related' or 'Probably Related'. Missing values for severity will be assigned as 'Severe' and missing value for relationship to treatment will be considered as 'Related' in the summary.

AEs leading to discontinuation of treatment are those with an action taken with study treatment on the AE CRF page of "Drug Withdrawn".

AEs leading to discontinuation from the study are those on the AE CRF page of "YES" to the question "Did the adverse event cause the subject to be discontinued from the study?".

By-subject listings will be provided for the following: All AEs, All TEAE, TEAEs leading to discontinuation of treatment and TEAEs leading to discontinuation of the study.

The duration of AEs will be derived as the AE end date (including imputation date for incomplete AE end date) – AE onset date (imputed date for incomplete AE onset date) +1.

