#### **7.3.2.6. Week 18 (Day 126) / End of Post-Treatment Efficacy Evaluation (or Early Termination during Post-treatment Efficacy Evaluation Period)**

The Week 18 / End of Post-treatment Efficacy Evaluation Visit is to occur at the end of Week 18 ( $\pm$  5 days), or for any subject that discontinues the study after the Week 6 Visit and prior to Week 18. The following procedures will be performed:

1. Question the subject and/or caregiver(s) about any changes to his/her health.
2. Review and question subject about any changes to his/her concomitant medications/treatments.
3. Obtain vital signs.
4. Perform wart assessments (refer to Section 7.4.1).
5. Perform clinical photography, if applicable (select centers only).
6. If subject achieved clearance of at least one treated wart **as determined by the PI or an appropriately qualified Sub-I** at Week 18 / End of Post-treatment Efficacy Evaluation visit, schedule the Follow-up visits (#1/Week 24 and #2/Week 30).
  - \* Remind the subject and/or caregiver(s) about restricted medications/treatments (refer to Section 7.6.10.1).

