#### Clinical Clearance:

Clinical clearance of a wart, **as determined by the PI or an appropriately qualified Sub-I**, should be recorded with a size of 0 mm and the subject should be instructed to stop applying study drug to that specific wart (spot) only.

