## **7.5.6. Adverse Events**

### **7.5.6.1. Definition of Adverse Event**

An adverse event (AE) means any untoward medical occurrence associated with the use of a drug in humans, whether or not considered drug related. An AE can therefore be any unfavorable and unintended sign (e.g., an abnormal laboratory finding), symptom, or disease temporally associated with the use of a drug, and does not imply any judgment about causality.

Any condition, event and/or signs and symptoms occurring after signing the informed consent form and before starting study drug treatment should be recorded as medical history in the eCRF. Medical conditions/diseases are considered AEs only if they worsen after starting study drug treatment (first application of study drug). Any clinically significant change from baseline, based upon the opinion of the investigator, in physical examination findings, vital signs, and/or laboratory values should be recorded as an AE.

**Study personnel should question and observe subjects for evidence of AEs paying particular attention to local application site reactions** and any potential cardiovascular or hematologic AEs. At each visit during the double-blind treatment and post-treatment efficacy evaluation period, the study site personnel should assess for the presence of local application site reactions and question the subject about AEs using an open question taking care not to influence the subject's (or caregiver's) answer, e.g., "Have you (or your child for caregivers) had any changes in your (or your child's) health since your last visit?"

Any AE, whether or not it is related to the test products, will be recorded in the source documents and reported on the appropriate eCRF page along with the date of onset, the severity, the relationship to the test product and the outcome. Under certain circumstances, additional information may be requested.

When an AE persists at the end of the study, the Investigator will ensure a follow-up of the subject until the Investigator/ Sponsor agree that the event is satisfactorily resolved or that no further follow-up is required.

Treatment emergent AEs (TEAEs) are defined as AEs whose onset occurs, severity worsens or intensity increases after receiving the study medication. Events which occur more than thirty days after the last dose of study medication will not be considered treatment emergent.

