#### **7.7.9. Safety Analysis**

Safety variables will be tabulated and presented for all patients in the Safety population. AEs will be categorized by system organ class and Preferred Term from the current version of MedDRA. AEs will be summarized overall, by seriousness, severity, and relationship to treatment. Incidence of AEs will be presented overall, by system organ class and preferred term. Severity and relationship to study drug of the incidence of AEs will also be presented. AEs causing study drug withdrawal and/or early study discontinuation and incidence of SAEs will be summarized.

Changes from baseline in vital signs and laboratory parameters, and shifts from baseline in laboratory parameters will be summarized by treatment. Descriptive statistics and frequency tables will be prepared as appropriate for laboratory measurements.

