### 4.1 Changes from Protocol

No changes as of this version of the SAP.

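### The SAP tabulates only treatment-emergent AEs, so at nominal dosing AEs starting on Days 73-126, which the protocol collects, get no incidence comparison by arm

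*SAP*

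**What the plan says.** **Collection.** The schedules in both documents mark AEs at every visit from Baseline to Week 18. Protocol 7.5.6.1 is explicit that this includes the period after treatment. It wants a check for local reactions where the gel was applied, together with an open question about AEs, and gives the timing as "At each visit during the double-blind treatment and post-treatment efficacy evaluation period". The last of these visits is "Week 18 (Day 126) / End of Post-Treatment Efficacy Evaluation".

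**Planned analysis in the protocol.** Protocol 7.7.9 states that "AEs will be summarized overall, by seriousness, severity, and relationship to treatment". It also plans incidence by SOC and preferred term, AEs causing drug withdrawal or early study discontinuation, and the incidence of SAEs. None of this is restricted to treatment-emergent events. The protocol does define a TEAE (7.5.6.1), with a 30-day limit after the final dose.

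**Planned analysis in the SAP.** SAP 12.6.1 repeats that limit ("but no more than 30 days after the last dose of study medication") and then adds a rule that the protocol does not contain: "Only TEAEs will be included in the summary tables". On changes from the protocol, SAP 4.1 says "No changes as of this version of the SAP".

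**Stopping drug on clearance.** When a wart is judged clear, "the subject should be instructed to stop applying study drug to that specific wart (spot) only" (Protocol 7.4.1.3).

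**The concern.** The protocol asks sites to look for harm, local site reactions in particular, for 12 weeks after treatment ends. The SAP then leaves most of that period out of the AE incidence tables and does not record this as a change.

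The restriction acts only at the late end. Protocol 7.5.6.1 records anything that occurs before the first application as medical history, so there are no pre-treatment AEs for a TEAE filter to remove. Its practical effect is to cut off late onsets.

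What is at stake is the comparison between arms. A listing shows each late event but gives no numerator and denominator by arm. Under the SAP as written:

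- an event on Day 80 that the investigator calls definitely related is absent from the treatment-related tables;
- a serious event on Day 90 is absent from the SOC/PT table of serious events;
- an AE on Day 100 that ends participation is absent from the table of TEAEs leading to study discontinuation. It would still count under the adverse-event reason in the disposition table (SAP 12.1), so the two tables can disagree.

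**Working it through.** **Inputs**

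- Nominal final dose: Day 42 (Protocol 7.6.2). The Week 6 visit window is ±3 days.
- End of AE collection: Day 126 (Protocol 7.3.2.6).
- TEAE limit: 30 days after the final dose (Protocol 7.5.6.1; SAP 8.0 and 12.6.1).

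**Check against a stated figure.** 126 − 42 = 84 days = 12 weeks, which matches the stated length of the post-treatment efficacy evaluation period. The documents do not state the cut-off day itself; it is derived here.

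**Cut-off and excluded days.** Last onset day counted = final dose day + 30.

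| Final dose | Last onset counted | Days excluded to Day 126 | Share of Days 1-126 | Share of Days 43-126 |
|---|---|---|---|---|
| Day 42 (nominal) | Day 72 | 54 | 54/126 = 43% | 54/84 = 64% |
| Day 39 (Week 6 − 3 days) | Day 69 | 57 | 45% | 68% |
| Day 45 (Week 6 + 3 days) | Day 75 | 51 | 40% | 61% |

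**Where the 54 days fall.** Between the Week 6 and Week 12 visits (Days 43-84), Days 43-72 are inside the window and Days 73-84 outside: 12 of 42 days, or 29%. Between Week 12 and Week 18 (Days 85-126) all 42 days are outside. 12 + 42 = 54.

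**Which outputs cover Days 73-126 at nominal dosing**

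| Output | Covers late onsets? |
|---|---|
| SOC/PT, severity, related and discontinuation tables (SAP 12.6.1) | No, TEAE only |
| Special-interest tables (SAP 12.6.1) | No, TEAE only |
| Serious events by SOC/PT (SAP 12.6.2) | No, labelled serious TEAEs |
| Treatment-related SAE summary (SAP 12.6.2) | Not stated |
| Deaths table (SAP 12.6.2) | Yes, deaths during the study |
| Vital signs by visit (SAP 12.6.4) | Yes, including Weeks 12 and 18 |
| Listings of all AEs, SAEs and deaths | Yes, by subject only |

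**Subjects who stop all dosing early.** If dosing ends at about Day 28, the cut-off is about Day 58 and 126 − 58 = 68 days are excluded. If it ends at about Day 14, the cut-off is about Day 44 and 82 days are excluded. The documents give no rate of complete clearance at Week 2 or Week 4. As an extreme bound, suppose every subject assumed to be clear at Week 18 (10% active, 2% vehicle; Protocol 7.7.2) had stopped at Day 14, which is 28 days early. The mean window would shorten by 0.10 × 28 = 2.8 days on active and 0.02 × 28 = 0.56 days on vehicle. The difference is 2.24 days in 72, about 3%.

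**The case against.** **The 30-day limit is the protocol's own.** It is prespecified in Protocol 7.5.6.1, a TEAE definition exists to be used in analysis, and Protocol 7.7.1 leaves detailed methods to the SAP. The unqualified term AEs in Protocol 7.7.9 can be read as shorthand for TEAEs. This stands in part: the definition is not an error and should stay. But the protocol nowhere confines its tables to TEAEs. If that was intended, the SAP should say so and why, rather than declare no change.

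**Late events are not lost.** All AEs, SAEs and deaths are listed. The limit is on onset, so a site reaction that starts during treatment and persists to Week 18 is counted. This stands, and it limits the point to the missing by-arm incidence.

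**Harm and benefit need not cover the same interval.** Nothing in the documents requires it, and by Week 18 the drug has been stopped for 12 weeks. That is a fair reason to keep TEAE tables as the main display. It does not explain why events collected on purpose in that period should have no incidence table at all.

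Three stronger readings are tempting and are not supported:

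- *Harm is tabulated only to about Day 72.* The deaths table and the vital-sign summaries run beyond that day.
- *About 43% of AEs are dropped.* That figure is a share of days. Turning it into a share of events needs an onset rate as high long after stopping as during daily application, and the documents give no onset pattern.
- *The response-dependent cut-off biases the arm comparison.* Drug is stopped wart by wart, so a subject with any uncleared wart keeps dosing and keeps the later cut-off. The window shortens only for subjects who stop all dosing before Week 6, and even the extreme bound is small.

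**Conclusion.** The point holds. At nominal dosing, AEs starting on Days 73-126 are collected but appear in no SOC/PT, severity, related, special-interest, discontinuation or main serious-event table by arm. That is 54 of 126 collection days and 54 of 84 post-treatment days. These counts assume a final dose on Day 42 and a Week 18 visit on Day 126. Moving the final dose within the Week 6 window gives 51 to 57 days.

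The share of AEs affected cannot be derived from the documents. No efficacy inference is touched. The earlier cut-off for subjects who stop all dosing before Week 6, including any whose treated warts have all cleared, is a minor further point. Its frequency is not given, and its effect on the arm comparison is probably small. The change should be made: the SAP narrows a summary that the protocol plans without restriction, and the remedy is cheap.

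**What to change.** 1. Keep the TEAE definition and all TEAE tables as planned.
2. In SAP 12.6.1, replace the sentence that restricts the summary tables to TEAEs.
3. Add by-arm tables for events with onset from first application to the Week 18 visit, using the same window for every subject whatever the final dose date: all AEs (overview and SOC/PT), related AEs, events of special interest, AEs leading to study discontinuation, and all SAEs.
4. In SAP 12.6.2, state which window each summary uses, in particular the treatment-related SAE summary, which carries no TEAE label.

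If the sponsor prefers TEAE-only tables, the least that is needed is to declare the restriction in SAP 4.1 and give the reason. That would settle the discrepancy but not supply the missing comparison.

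The cost is a few extra tables from data already collected. Their drawback is that they will contain more background events unrelated to treatment, which is why they should sit beside the TEAE tables and not replace them.
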